5.2 Exclusion criteria

Medical conditions

1. Subjects with either the history of hypersensitivity to excipients of the study drug or to drugs with a similar chemical structure or class to the study drug OR
2. pregnant and/or lactating women OR
3. Patients with a previously or currently diagnosed MDS/ AML or pneumonitis OR
4. Patients who have not recovered sufficiently from prior surgery or anticancer treatment OR
5. Patients who have known history of hepatitis B or hepatitis C OR
6. Patients with active infection such as TB

Prior/concurrent clinical study experience

7. Participation in another clinical study with a study drug administered in the last 3 months

Other exclusions

8. Judgment by the investigator that the subject should not participate in the study if the subject is unlikely to comply with study procedures, restrictions and requirements.
9. Previous enrolment in the present study.

5.3 Lifestyle restrictions

5.3.1 Meals and dietary restrictions

No specific dietary restrictions will be imposed on subjects recruited for this study. Co-administration with food slowed the rate of absorption but did not significantly affect the extent of absorption of olaparib. Consequently, patients should take Lynparza without regard to food.

5.3.2 Caffeine, alcohol, and tobacco

No specific restrictions will apply.

5.3.3 Activity

There are no specific restrictions that will apply.

5.4 Screen failures

Screen failures are defined as subjects who signed the informed consent form to participate in the clinical study but are not subsequently entered in the study. A minimal set of screen failure information is required to ensure transparent reporting of screen failure subjects to meet the

Consolidated Standards of Reporting Trials (CONSORT) publishing requirements and to respond to queries from regulatory authorities. Minimal information includes demography, screen failure details, eligibility criteria, and any serious adverse event (SAE).

Individuals who do not meet the criteria for participation in this study (screen failure) shall not be rescreened.

These subjects should have the reason for study withdrawal recorded in the eCRF.

6. STUDY TREATMENTS

Study treatment is defined as any study drug(s) (including marketed product comparator and placebo) or medical device(s) intended to be administered to a study participant according to the study protocol. Study treatment in this study refers to Olaparib.

6.1 Treatments administered

6.1.1 Study Drug

Table 4 Study Drug particulars

Study Treatment	
Study treatment name:	Olaparib
Dosage formulation:	Tablets
Route of administration	Oral
Dosing instructions:	The recommended dose of olaparib is 300 mg (two 150 mg tablets) taken twice daily, equivalent to a total daily dose of 600 mg. The 100 mg tablet is available for dose reduction
Packaging and labelling	Study treatment will be provided in a bottle. Each bottle will be labelled in accordance with Good Manufacturing Practice (GMP) Annex 13 and per Indian regulatory requirement.
Provider	AstraZeneca's Pharmaceutical Development, R&D Supply Chain will supply olaparib to the Investigator as green film-coated tablets.

6.2 Preparation/handling/storage/accountability

The investigator or designee must confirm appropriate temperature conditions have been maintained during transit for all study treatment received and any discrepancies are reported and resolved before use of the study treatment.

Only subjects enrolled in the study may receive study treatment and only authorised site staff may supply or administer study treatment. The study treatment must be stored in a secure, environmentally controlled, and monitored area in accordance with the labelled storage conditions with access limited to the investigator and authorised site staff.

The investigator, institution, or the head of the medical institution (where applicable) is responsible for study treatment accountability, reconciliation, and record maintenance (i.e., receipt, reconciliation, and final disposition records).

The Dispensing and retention of reserve samples of the study treatment will be performed in accordance with the local Indian regulations.

6.3 Measures to minimise bias: randomisation and blinding

If a subject withdraws from the study, then they will not be replaced.

The National co-ordinating investigator and any person appointed by him/her will have access to the patient level data. The appointed CRO shall help in the analysis but will not have access to the patient particulars. AstraZeneca employees shall not be in possession of patient level data at any time.

Open-label, single arm study. No blinding at site level *This is an open-label study; potential bias will be reduced by the following steps: 1) Consecutive subjects fitting into the inclusion criteria from the respective sites shall be enrolled in an effort to reduce selection bias in enrolment.*

6.4 Treatment compliance

Any change in the dosing schedule, dose interruptions, dose reductions or dose discontinuations should be recorded in the eCRF.

The investigator(s) shall be responsible for ensuring that the subject has returned all the unused study drug.

6.5 Concomitant therapy

Any medication or vaccine, including over the counter or prescription medications, vitamins and/or herbal supplements that the subject is receiving at the time of enrolment or receives during the study must be recorded along with:

- Reason for use
- Dates of administration including start and end dates
- Dosage information

6.5.1 Other concomitant treatment

Any medication other than that described above, which is considered necessary for the subject's safety and wellbeing, may be given at the discretion of the Investigator and recorded in the appropriate sections of the Case Report Form.

The use of any natural/herbal products or other traditional remedies should be discouraged, but use of these products, as well as use of all vitamins, nutritional supplements, and all other concomitant medications must be recorded in the case report form (CRF).

Medications that may NOT be administered

No other anti-cancer therapy (chemotherapy, immunotherapy, hormonal therapy (Hormone replacement therapy (HRT) is acceptable), radiotherapy, biological therapy or other novel agent) is to be permitted while the patient is receiving study medication.

Live virus and live bacterial vaccines should not be administered whilst the patient is receiving study medication and during the 30 day follow up period. An increased risk of infection by the administration of live virus and bacterial vaccines has been observed with conventional chemotherapy drugs and the effects with olaparib are unknown.

Restricted concomitant medications

Strong or Moderate CYP3A inhibitors

Known strong CYP3A inhibitors (e.g., itraconazole, telithromycin, clarithromycin, boosted protease inhibitors, indinavir, saquinavir, nelfinavir, boceprevir, telaprevir) or moderate CYP3A inhibitors (ciprofloxacin, erythromycin, diltiazem, fluconazole, verapamil) should not be taken with olaparib.

If there is no suitable alternative concomitant medication, then the dose of olaparib should be reduced for the period of concomitant administration. The dose reduction of olaparib should be recorded in the CRF with the reason documented as concomitant CYP3A inhibitor use.

- Strong CYP3A inhibitors – reduce the dose of olaparib to 100 mg bd for the duration of concomitant therapy with the strong inhibitor and for 5 half-lives afterwards.
- Moderate CYP3A inhibitors - reduce the dose of olaparib to 150 mg bd for the duration of concomitant therapy with the moderate inhibitor and for 3 half-lives afterwards.

- After the washout of the inhibitor is complete, the olaparib dose can be re-escalated.

Strong or Moderate CYP3A inducers

Strong (e.g., phenobarbital, phenytoin, rifampicin, rifabutin, rifapentine, carbamazepine, nevirapine, enzalutamide and St John's Wort) and moderate CYP3A inducers (eg. bosentan, efavirenz, modafinil) of CYP3A should not be taken with olaparib.

If the use of any strong or moderate CYP3A inducers are considered necessary for the patient's safety and welfare this could diminish the clinical efficacy of olaparib.

If a patient requires use of a strong or moderate CYP3A inducer then they must be monitored carefully for any change in efficacy of olaparib.

P-gp inhibitors

It is possible that co-administration of P-gp inhibitors (eg amiodarone, azithromycin) may increase exposure to olaparib. Caution should therefore be observed.

Effect of olaparib on other drugs

- Based on limited in vitro data, olaparib may increase the exposure to substrates of CYP3A4, P-gp, OATP1B1, OCT1, OCT2, OAT3, MATE1 and MATE2K.
- Based on limited in vitro data, olaparib may reduce the exposure to substrates of CYP3A4, 2B6, 2C9, 2C19 and P-gp.
- The efficacy of hormonal contraceptives may be reduced if co administered with olaparib.
- Caution should therefore be observed if substrates of these isoenzymes or transporter proteins are co-administered. Examples of substrates include:
 - CYP3A4 – hormonal contraceptive, simvastatin, cisapride, cyclosporine, ergot alkaloids, fentanyl, pimozide, sirolimus, tacrolimus and quetiapine
 - CYP2B6 – bupropion, efavirenz
 - CYP2C9 – warfarin
 - CYP2C19 - lansoprazole, omeprazole, S-mephenytoin
 - P-gp - simvastatin, pravastatin, digoxin, dabigatran, colchicine
 - OATP1B1 - bosentan, glibenclamide, repaglinide, statins and valsartan
 - OCT1, MATE1, MATE2K – metformin
 - OCT2 - serum creatinine
 - OAT3 -furosemide, methotrexate

Anticoagulant Therapy

Patients who are taking warfarin may participate in this trial; however, it is recommended that international normalised ratio (INR) be monitored carefully at least once per week for the first month, then monthly if the INR is stable. Subcutaneous heparin and low molecular weight heparin are permitted.

Anti-emetics/Anti-diarrhoeals

From visit 2 onwards, should a patient develop nausea, vomiting and / or diarrhoea, then these symptoms should be reported as AEs (see section 8.3) and appropriate treatment of the event given.

Palliative radiotherapy

Palliative radiotherapy may be used for the treatment of pain at the site of bony metastases that were present at baseline, provided the investigator does not feel that these are indicative of clinical disease progression during the study period. Study treatment should be discontinued for a minimum of 3 days before a patient undergoes therapeutic palliative radiation treatment. Study treatment should be restarted within 4 weeks as long as any bone marrow toxicity has recovered.

Administration of other anti-cancer agents

Patients must not receive any other concurrent anti-cancer therapy, including investigational agents, while on study treatment. Patients may continue the use of bisphosphonates or denosumab for bone disease and corticosteroids for the symptomatic control of brain metastases provided the dose is stable before and during the study and they were started at least 4 weeks prior to beginning study treatment.

Other concomitant treatment

Other medication other than that described above, which is considered necessary for the patient's safety and wellbeing, may be given at the discretion of the Investigator and recorded in the appropriate sections of the Case Report Form.

In addition, any unplanned diagnostic, therapeutic or surgical procedure performed during the study period must be recorded in the eCRF.

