6.6 Dose modification

This protocol allows for some alteration from the currently outlined dosing schedule, but the maximum daily dose shall not exceed 300 mg BD. Dose modifications are permitted in case of AE's as per section 8.4.6.

In case a dose reduction is necessary, the Study treatment will be administered as follows:

Table 5: Dose Reduction Schedule

Initial dose	Following re-challenge post interruption: Dose reduction 1	Dose reduction 2
300 mg twice daily	250 mg Twice daily	200 mg twice daily (lowest allowable dose level)

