8.4.5 Management of study drug - related toxicities, dose interruptions and dose reductions

Toxicity observed during the course of the study could be managed by interruption of the dose of study treatment or dose reductions. Repeat dose interruptions are allowed as required, for a maximum of 4 weeks on each occasion. If the interruption is any longer, the study team must be informed. Study treatment can be dose reduced to 250 mg twice daily as a first step and to 200 mg twice daily as a second step. If the reduced dose of 200 mg twice daily is not tolerable, no further dose reduction is allowed and study treatment should be discontinued.

Once dose is reduced, escalation is not permitted.

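### The CYP3A-inhibitor dose rules in 6.5.1 conflict in wording with the dose floor in Table 5 and the no-escalation rule in 8.4.5, and a subject already reduced for toxicity is left without a clear rule

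*Protocol*

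**What the plan says.** **Interaction rule, Protocol 6.5.1.** Strong and moderate CYP3A inhibitors are to be avoided. If there is no suitable substitute, the instruction for a strong inhibitor is "reduce the dose of olaparib to 100 mg bd for the duration of concomitant therapy with the strong inhibitor and for 5 half-lives afterwards", and for a moderate one "reduce the dose of olaparib to 150 mg bd for the duration of concomitant therapy with the moderate inhibitor and for 3 half-lives afterwards". After that, "After the washout of the inhibitor is complete, the olaparib dose can be re-escalated". The reason is captured: "The dose reduction of olaparib should be recorded in the CRF with the reason documented as concomitant CYP3A inhibitor use".

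**Dose modification, Protocol 6.6.** "Dose modifications are permitted in case of AE's as per section 8.4.6". The sentence that introduces Table 5 applies the table whenever a reduction is needed and names no cause. The steps run from 300 to 250 to 200 mg bd, and the last is labelled "200 mg twice daily (lowest allowable dose level". The maximum is 300 mg bd.

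**Toxicity management, Protocol 8.4.5.** The same two steps are given. If 200 mg bd is not tolerated, treatment is discontinued. The section closes with "Once dose is reduced, escalation is not permitted".

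**Related places.** Section 7.1.1 mentions reduction to 200 mg bd in connection with adverse events. Section 8.4.6.3, whose heading concerns interruptions not related to toxicity, also sends the reader to Table 5 for the reduction schedule.

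**The concern.** Taken at face value, 6.5.1 prescribes two doses that Table 5 does not allow and a return to a higher dose that 8.4.5 forbids. Neither 6.6 nor 8.4.5 mentions 6.5.1, and 6.5.1 mentions neither of them. A site has to work out for itself which rule governs.

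Safety is the trial's only objective, and its results are adverse-event rates in subjects taking olaparib. If sites resolve the wording differently, the dose behind those rates differs by site for reasons unrelated to tolerability. Reductions made for a drug interaction may also be counted with reductions made for toxicity. For a subject whose dose was lowered because she did not tolerate a higher one, the unanswered question of where the dose may return bears on her safety.

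**Working it through.** No stated statistical figure depends on these passages, so the check is a comparison of rules.

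**Step 1: dose levels (bd dose x 2 = daily total).**

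| Source | Level | Daily total | Below the 200 mg bd floor? |
|---|---|---|---|
| 6.5.1, strong inhibitor | 100 mg bd | 200 mg | yes |
| 6.5.1, moderate inhibitor | 150 mg bd | 300 mg | yes |
| Table 5, second reduction | 200 mg bd | 400 mg | it is the floor |
| Table 5, first reduction | 250 mg bd | 500 mg | no |
| Table 5, initial dose | 300 mg bd | 600 mg | no |

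Both interaction doses are below the floor.

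**Step 2: escalation.** 6.5.1 permits it after washout. 8.4.5 forbids it after a reduction and writes no exception. 6.6 supplies the floor but contains no escalation ban; the ban stands only in 8.4.5.

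**Step 3: does the text limit the floor and the ban to toxicity?**
- For a limit: 8.4.5 is headed and opened as toxicity management, 6.6 speaks of adverse events, a Table 5 column refers to re-challenge after an interruption, and 7.1.1 links 200 mg bd to adverse events.
- Against a limit: the sentence introducing Table 5 names no cause, the last sentence of 8.4.5 is unqualified, and 8.4.6.3 refers to Table 5 under a non-toxicity heading. That last pointer is weak evidence, since it follows a remark about olaparib adverse events.
- If 6.6 is read as covering adverse events alone, the section headed Dose modification is silent on the reductions that 6.5.1 requires.

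The limit is a reasonable inference, but it is not stated.

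**Step 4: two kinds of subject.**

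*Never reduced for toxicity.* With the limit inferred, only 6.5.1 applies: 300 mg bd, down to 100 or 150 mg bd, then up again. Most of the conflict disappears.

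*Already at 250 or 200 mg bd for toxicity.* The limit does not settle her case, because she has had a toxicity reduction and now has an interaction reduction too. After washout the wording leaves open:
- a return to her toxicity-reduced level, which is compatible with 6.5.1 and with a ban read as concerning toxicity;
- a return towards 300 mg bd, which stays within the 6.6 maximum and the bare word in 6.5.1 but goes against 8.4.5;
- no rise at all, if 8.4.5 is taken literally.

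The fixed interaction levels are also the same whatever dose she came from. As a share of the previous nominal dose:

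| Previous dose | 100 mg bd | 150 mg bd |
|---|---|---|
| 300 mg bd | 100/300 = 33% | 150/300 = 50% |
| 250 mg bd | 100/250 = 40% | 150/250 = 60% |
| 200 mg bd | 100/200 = 50% | 150/200 = 75% |

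These are ratios of nominal dose only. They show that 6.5.1 does not say whether or how an earlier reduction counts.

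**Step 5: sample size.** The stated basis is p = 0.40, margin 0.07 and a 95% interval: 1.96² x 0.40 x 0.60 / 0.07² = 188.2, rounded up to 189, which agrees with the stated figure of approximately 190. The dosing text does not enter it.

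**The case against.** The strongest reply is scope. The escalation ban appears once, at the end of a section on toxicity, and the floor sits in text about adverse events. Section 6.5.1 is complete in itself, with its own trigger, level, duration, return and recorded reason. A sensible site would follow it for an interaction and follow 8.4.5 for toxicity. To re-escalate ordinarily means to go back to the earlier level, so a toxicity-reduced subject could return to that level without breaking either rule. The inhibitors are to be avoided in any case, so few subjects may be involved, and dose-reduction counts are not a listed endpoint.

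Much of this stands. For a subject never reduced for toxicity, the scope reading is the likely intent. It remains an inference, and for the toxicity-reduced subject it depends on a meaning of re-escalation that the protocol does not spell out.

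Several stronger readings are tempting but unsupported:
- *The protocol gives one subject several incompatible dose courses.* It assigns no such set; they are competing readings of unlinked text.
- *A dose below the floor means stopping treatment.* 8.4.5 calls for discontinuation only when 200 mg bd is not tolerated, and no passage extends this to interaction doses.
- *An interaction dose in a toxicity-reduced subject recreates an exposure she did not tolerate.* This needs a pharmacokinetic equivalence that the protocol does not state, and the trial measures no pharmacokinetics.

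**Conclusion.** The point holds as an internal inconsistency in the dosing rules. As written, 6.5.1 conflicts with Table 5 on the floor and with 8.4.5 on escalation, and nothing in the document sets precedence. Reading the floor and the ban as toxicity rules removes most of the conflict for subjects never reduced for toxicity. It does not settle the case of a subject already at 250 or 200 mg bd who then needs an inhibitor.

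The size cannot be put as a number: the protocol does not give the share of subjects who will need a strong or moderate inhibitor, or who will need one after a toxicity reduction. The sample size and the primary summaries of adverse events are not invalidated. What is affected is consistency of dosing across sites, the classification of dose reductions, and the safety of a probably small group. It is a wording reconciliation that is worth making, not a flaw that undermines the trial. No view is taken on which dose or rule is right.

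**What to change.** Reconcile 6.5.1, 6.6 with Table 5, 8.4.5 and 8.4.6.3, with the clinical team choosing the rules:

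1. State which reductions the Table 5 floor covers and which the no-escalation rule covers: toxicity reductions only, or all reductions. Amend the other passages to match.
2. Add cross-references to 6.5.1 in 6.6 and 8.4.5, and make the pointer in 8.4.6.3 consistent with the scope chosen.
3. State how 6.5.1 applies to a subject already reduced for toxicity: what the interaction levels are for her, and the highest level to which she may return after washout.
4. Summarise interaction-driven reductions separately from toxicity-driven ones, using the reason that 6.5.1 already requires in the CRF.

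The cost is amendment wording, a short memo to sites and one additional split in the reduction summaries. No new data, visits or subjects are needed.

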6.5.2 Rescue medication

The study site shall not supply rescue medication as a part of this study. In case of AE's, please refer to section 8.4.5 and 8.4.6 for the management of drug related toxicities.

6.6 Dose modification

This protocol allows for some alteration from the currently outlined dosing schedule, but the maximum daily dose shall not exceed 300 mg BD. Dose modifications are permitted in case of AE's as per section 8.4.6.

In case a dose reduction is necessary, the Study treatment will be administered as follows:

Table 5: Dose Reduction Schedule

Initial dose	Following re-challenge post interruption: Dose reduction 1	Dose reduction 2
300 mg twice daily	250 mg Twice daily	200 mg twice daily (lowest allowable dose level)

6.7 Treatment after the end of study (Post Trial Access to Olaparib)

Subjects receiving olaparib at the time of study completion (i.e. after completion of Treatment Phase) may continue to receive olaparib, if in the opinion of their treating physician they are continuing to derive clinical benefit from continued treatment or have not progressed clinically. These subjects shall receive the study drug free of cost under a separate compassionate use program and will not receive the medication via the clinical trial supply for this study. These subjects shall not be actively monitored for AE's and it will be the responsibility of the treating physician to ensure reporting of all SAE's, pregnancies, overdose and medication errors to the relevant authorities as per the standard practice in India.

DISCONTINUATION OF TREATMENT AND SUBJECT WITHDRAWAL

7.1 Discontinuation of study treatment

Subjects may be discontinued from olaparib in the following situations. Note that discontinuation from study treatment is NOT the same thing as a complete withdrawal from the study

- Disease Progression: Disease progression can be considered as a worsening of a subject's condition attributable to the disease for which the study drug is being studied. It may be an increase in the severity of the disease under study (DUS) and/or increases in the signs and symptoms of the cancer. The development of new, or progression of existing metastasis to the primary cancer under study should be considered as disease progression and not an AE (if the progression was 'as expected'). Events, which are unequivocally due to disease progression, should not be reported as an AE during the study. All the events occurring at the Indian sites that meet the criteria for seriousness will be reported expeditiously as SAEs per local regulatory requirements to the Indian regulatory authority and the concerned ethics committees. In this study, disease progression shall be determined by the investigator as per the guidelines currently being followed by the site for the indication in question. Progression of disease assessed radiographically should occur in comparison to baseline imaging obtained during screening.

- Adverse Event (including laboratory abnormality or intercurrent illness) which, in the opinion of the investigator, indicates that continued participation in the study is not in the best interest of the subject
- The subject (or the subject's legally acceptable representative) withdraws consent for administration of study drug
- ILD/Pneumonitis
- Acute myeloid leukemia/Myelodysplastic syndrome or other de novo malignancy requiring active treatment
- Pregnancy
- Any adverse event deemed to be related to olaparib that requires a dose hold of more than 21 days will result in permanent discontinuation of olaparib.
- Grade 3 or higher adverse reaction that does not improve to Grade 0-2 after withholding for up to 3 weeks
- Severe non-compliance with the Clinical Study Protocol
- The patient has a confirmed positive serum pregnancy test

See the SoA for data to be collected at the time of treatment discontinuation and follow-up and for any further evaluations that need to be completed.

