7.1.1 Rechallenge

Rechallenge with Olaparib in this study is not allowed. Due to adverse events, the maximum dose can be reduced to 200 mg BD as per section 8.4.6. However, if drug discontinuation is necessary, the subject shall not be restarted on Olaparib subsequently.

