7.1.2 Procedures for discontinuation of study treatment

The investigator should instruct the subject to contact the site before or at the time if Study treatment is stopped. A subject that decides to discontinue Study treatment will always be asked about the reason(s) and the presence of any AEs. The date of last intake of Study treatment should be documented in the eCRF. All Study treatment should be returned by the subject at their next on-site study visit or unscheduled visit. Subjects permanently discontinuing Study treatment should be given locally available standard of care therapy, at the discretion of the Investigator.

Discontinuation of Study treatment, for any reason, does not impact on the subject's participation in the study. The subject should continue attending subsequent study visits and data collection should continue according to the study protocol. If the subject does not agree to continue in-person study visits, a modified follow-up must be arranged to ensure the collection of endpoints and safety information. This could be a telephone contact with the subject at 28 days post discontinuation

(End of Study Visit as described in SoA), a contact with a relative or treating physician, or information from medical records. The approach taken should be recorded in the medical records. A subject that agrees to modified follow-up is not considered to have withdrawn consent or to have withdrawn from the study.

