8. STUDY ASSESSMENTS AND PROCEDURES

Study procedures and their timing are summarised in the SoA.

The investigator will ensure that data are recorded on the electronic Case Report Forms

The investigator ensures the accuracy, completeness, for eCRFs include: legibility and timeliness of the data recorded and of the provision of answers to data queries according to the Clinical Study Agreement. The investigator will sign the completed electronic Case Report Forms. A copy of the completed electronic Case Report Forms will be archived at the study site.

Immediate safety concerns should be discussed with the sponsor immediately upon occurrence or awareness to determine if the subject should continue or discontinue Study treatment.

Adherence to the study design requirements, including those specified in the SoA, is essential and required for study conduct.

All screening evaluations must be completed and reviewed to confirm that potential subjects meet all eligibility criteria. The investigator will maintain a screening log to record details of all subjects screened and to confirm eligibility or record reasons for screening failure, as applicable.

Procedures conducted as part of the subject's routine clinical management (e.g., blood count) and obtained before signing of the ICF may be utilised for screening or baseline purposes provided the procedures met the protocol-specified criteria and were performed within the time frame defined in the SoA.

The maximum amount of blood collected from each subject over the duration of the study, including any extra assessments that may be required, will not exceed 10 mL. Repeat or unscheduled samples may be taken for safety reasons or for technical issues with the samples.

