8.4.5.1 Management of haematological toxicity

Management of anaemia

Table 7 Management of Anaemia

Haemoglobin	Action to be Taken
Hb < 10 but \geq 8 g/dl (CTCAE Grade 2)	Give appropriate supportive treatment and investigate causality. Investigator judgement to continue olaparib with supportive treatment (eg transfusion) or interrupt dose for a maximum of 4 weeks. If repeat Hb < 10 but \geq 8 g/dl, dose interrupt (for max of 4 weeks) until Hb \geq 10 g/dl and upon recovery dose reduction to 250 mg twice

	daily as a first step and to 200 mg twice daily as a second step may be considered.
Hb < 8 g/dl (CTCAE Grade 3)	Give appropriate supportive treatment (e.g. transfusion) and investigate causality. Interrupt olaparib for a maximum of 4 weeks, until improved to Hb \geq 10 g/dl. Upon recovery dose reduce to 250 mg twice daily as a first step and to 200 mg twice daily as a second step in the case of repeat Hb decrease

Common treatable causes of anaemia (e.g., iron, vitamin B12 or folate deficiencies and hypothyroidism) should be investigated and appropriately managed. In some cases, management of anaemia may require blood transfusions. For cases where subjects develop prolonged haematological toxicity (\geq 2-week interruption/delay in study treatment due to CTC grade 3 or worse anaemia and/or development of blood transfusion dependence), refer to Section 8.4.5.3 for the management of this.

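### A related olaparib hold of 22 to 28 days means permanent discontinuation under section 7.1 but may continue and end in restart under sections 8.4.5 to 8.4.6

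*Protocol*

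**What the plan says.** Section 7.1 lists the grounds for stopping olaparib, and two of them carry a three-week limit. A related adverse event that "requires a dose hold of more than 21 days will result in permanent discontinuation of olaparib". A separate ground is a "Grade 3 or higher adverse reaction that does not improve to Grade 0-2 after withholding for up to 3 weeks". Section 7.1.1 makes the stop final: "if drug discontinuation is necessary, the subject shall not be restarted on Olaparib subsequently". The same section also states, without qualification, that rechallenge is not permitted.

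Section 8.4.5, headed as the management of drug-related toxicity, sets a longer limit: "Repeat dose interruptions are allowed as required, for a maximum of 4 weeks on each occasion". Beyond that, "If the interruption is any longer, the study team must be informed". The subsections repeat the 4-week figure:

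- Table 7, for haemoglobin below 8 g/dL: "Interrupt olaparib for a maximum of 4 weeks, until improved to Hb" of at least 10 g/dL, then restart at 250 mg twice daily, with 200 mg as a second step.
- Table 8, for Grade 3-4 neutropenia, leukopenia or thrombocytopenia: hold for up to 4 weeks until Grade 1 or better.
- Section 8.4.5.3: haematologist referral, and the stop for counts not back to Grade 1 or better, are both set at 4 weeks of interruption.
- Section 8.4.6, for non-haematological toxicity: the same 4 weeks per occasion, with notice to the study monitor if longer. It presupposes re-challenge after an interruption, as does Table 5 in section 6.6.

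**The concern.** The two sets of rules cover the same events. Section 7.1 applies to any event judged related to olaparib, and section 8.4.5 is written for drug-related toxicity. They set different limits and different consequences, and the protocol does not say which prevails.

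At stake is whether a recovering patient may resume treatment. She is off drug on hold days 22 to 28 under either rule. Under section 7.1 she can never restart; under section 8.4 she may. A site that reads section 8.4 has no prompt to consult anyone at day 22, because its notification duties begin only after 4 weeks.

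**Working it through.** The protocol gives no figure on this point. Its one computed number, the sample size in section 9.2, reproduces: 1.96² × 0.40 × 0.60 / 0.07² = 188.2, rounded up to 189, against about 190 stated. The conflict does not touch it.

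**Step 1: the limits in days.** Section 7.1 stops treatment when the hold exceeds 21 days, so from hold day 22. Sections 8.4.5 to 8.4.6 allow 4 × 7 = 28 days. The days above 21 and not above 28 are 22, 23, 24, 25, 26, 27 and 28: a band of 28 − 21 = 7 days.

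**Step 2: the rules side by side for a related event.**

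| Hold day | Section 7.1 | Sections 8.4.5 to 8.4.6 |
|---|---|---|
| up to 21 | hold permitted | hold permitted, restart on recovery |
| 22 to 28 | permanent stop, no restart | hold permitted, restart on recovery |
| after 28 | permanent stop, no restart | blood counts not at Grade 1 or better: stop (8.4.5.3); non-haematological: inform the study monitor (8.4.6) |

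For non-haematological events the disagreement therefore continues past day 28.

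**Step 3: a worked case.** A patient has related Grade 3 anaemia (haemoglobin below 8 g/dL) and olaparib is held. On hold day 21 her haemoglobin is between 8.0 and 9.9 g/dL.

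- Table 7 labels this range Grade 2. She has improved to within Grade 0-2, so the three-week grade ground in section 7.1 is not met.
- She is still below the 10 g/dL that Table 7 requires for restart, so Table 7 continues the hold up to day 28 and then restarts at 250 mg twice daily if she recovers.
- The 21-day ground in section 7.1 ends olaparib permanently on day 22.

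**Step 4: the recovery standard.** Section 7.1 asks for Grade 0-2 at 3 weeks after a Grade 3 or higher reaction. Section 8.4.5.3 asks for Grade 1 or better at 4 weeks for blood counts. The two sections differ in recovery level as well as in time.

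**Step 5: effect on the primary endpoint.** Table 3 counts subjects with adverse events and serious adverse events. A subject in the conflict band already has a related adverse event, so she is already in the any-event numerator. Discontinuation rate is not a listed endpoint.

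**The case against.** The best defence is that 4 weeks is a maximum. A site that stops at day 22 breaches no ceiling, so the stricter rule could serve as the default. That is a workable practice, but it does not reconcile the text: for related events, Table 7's restart after a hold of 22 to 28 days and the 4-week stop in section 8.4.5.3 could never operate as written.

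Tables 7 and 8 also call for causality to be investigated, so the 4-week limit can apply without conflict while causality is open or once the event is judged unrelated. This stands, and it confines the point to related events. Interruptions for reasons other than toxicity (section 8.4.6.3) are likewise outside it.

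Two other escapes fail. The sentence introducing the list in section 7.1 is permissive, but the 21-day ground has its own mandatory wording. Section 8 asks for immediate safety concerns to be discussed with the sponsor "to determine if the subject should continue or discontinue Study treatment", but it ranks neither rule.

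A reader might infer that the primary safety result is biased, or that months of adverse-event data are lost. The documents do not support either. The any-event proportion barely moves. After discontinuation, section 7.1.2 says: "The subject should continue attending subsequent study visits and data collection should continue according to the study protocol". Section 9.4.2 does limit the summaries to 28 days after the last dose, but a later window after restart mostly reflects added time on drug. Its length depends on how long she then stays on treatment, which cannot be known in advance.

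**Conclusion.** The contradiction is in the protocol as written. For a related hold of 22 to 28 days, one section requires a permanent stop and another permits a continued hold and restart. For non-haematological events the disagreement runs beyond day 28. The consequence is inconsistent patient management, exposure and permanent discontinuation across sites. Because a stop cannot be reversed, it deserves correction even though this single-arm, descriptive trial's main proportions are little affected.

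The conclusion rests on taking 4 weeks as 28 days and on the event being judged related. The number of subjects affected cannot be computed, because the protocol gives no distribution of hold lengths.

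A reader might also infer that the 21-day rule is the error and should simply be relaxed. The protocol does not show which limit was intended. It ties treatment to the local prescribing information (sections 4.1 and 4.3), which is not reproduced, so the choice belongs to the sponsor.

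**What to change.** The sponsor should choose one limit, consistent with the local prescribing information, and apply it throughout:

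- **Four weeks:** in section 7.1 change both 21 days and 3 weeks to 4 weeks, and state that blood counts follow the Grade 1 recovery rule of section 8.4.5.3; or
- **Twenty-one days:** change 4 weeks to 21 days in section 8.4.5, Tables 7 and 8, section 8.4.5.3 and section 8.4.6.

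With either choice:

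- State one consequence when a related hold passes the limit: permanent stop, replacing the notify-only wording in sections 8.4.5 and 8.4.6 for related events.
- Amend section 7.1.1 to say that restart after a permitted interruption is allowed and only restart after permanent discontinuation is barred, in line with Table 5 and section 8.4.6. Without this, the restart wording would still conflict.

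The cost is a wording amendment with ethics committee approval (Appendix A 1) and a communication to the 15 sites. No new data are needed: the eCRF already records interruptions, reductions and their reasons (sections 6.4 and 8.4.6.3), so affected subjects can be identified. It should be done early, because a patient stopped under section 7.1 cannot be restarted.
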